6.4.2. Additional considerations

Safety analysis will be done per administered dose. Subjects who missed reporting symptoms (solicited/unsolicited or concomitant medications) will be treated as subjects without symptoms (solicited/unsolicited or concomitant medications, respectively). A sensitivity analysis will be performed on documented doses i.e. accounting only for doses where solicited symptoms are indicated as being absent/present in case more than 5% of the doses are not documented.

AE relationship to vaccination is defined as the relationship to at least one study vaccine as identified by the investigator. In case the related vaccine has not been specified the adverse event will be considered related to all study vaccines. The percentage of subjects reporting of causally related solicited symptoms and unsolicited adverse events within the 31-day (Days 1-31) post-vaccination period will be provided by group for each study vaccine separately.

The planned analysis of the percentage of doses and of subjects reporting at least one grade 3 causally related symptom (solicited or unsolicited) during the 8 day (Day 1-Day 8) solicited follow-up period post-vaccination will not be generated considering this analysis is of limited clinical relevance and is not part of the standard analyses planned in other PCV free Rota studies.

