10.3. Determination of sample size

The target sample size is 832 subjects evaluable for immunogenicity analyses at Visit 4 (416 subjects in each group). Assuming that approximately 35% of enrolled subjects might withdraw or not be evaluable for analyses of immunogenicity, the target sample size to be enrolled is 1280 subjects (640 subjects in each group).

The primary objective of this study is to demonstrate the immune response elicited to all antigens contained in each of the routine infant vaccines *Pediarix*, *Hiberix* and *Prevenar 13* when co-administered with PCV-free liquid HRV vaccine is non-inferior to that elicited when co-administered with the lyophilized HRV vaccine.

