10.5. Derived and transformed data

- A seronegative subject is a subject whose antibody concentration is below the cut-off value.
- A seropositive subject is a subject whose antibody concentration is greater than or equal to the cut-off value. The applicable thresholds are presented in [Table 7](#).
- A seroprotected subject is a subject whose antibody concentration is greater than or equal to the level defining clinical protection. The following seroprotection thresholds are applicable:
 - anti-D antibody concentrations ≥ 0.1 IU/mL.
 - anti-T antibody concentrations ≥ 0.1 IU/mL.
 - anti-HBs antibody concentrations ≥ 10 mIU/mL.
 - anti-poliovirus types 1, 2 and 3 antibody titers ≥ 8 ED50.
 - anti-PRP antibody concentrations ≥ 0.15 μ g/mL.
- Other cut-offs to be considered:
 - anti RV IgA antibody concentration ≥ 90 U/mL.
 - anti-pneumococcal serotypes (1, 3, 4, 5, 6A, 6B, 7F, 9V, 14, 18C, 19A, 19F, 23F) antibody concentrations ≥ 0.35 μ g/mL for the ELISA.
 - anti-PRP antibody concentrations ≥ 1.0 μ g/mL.
- The GMC calculation will be performed by taking the anti-log of the mean of the log concentration transformations. Note that antibody concentrations below the cut-off of the assay will be given an arbitrary value of half the cut-off while antibody concentration above the assay cut-off but below the Limit of Quantification will be given the assay cut-off as value.

Handling of missing data:

Immunogenicity:

- For a given subject and a given immunogenicity measurement, missing or non-evaluable measurements will not be replaced.

Reactogenicity and Safety:

- For analysis of solicited, unsolicited AEs (such as SAEs or AEs by primary MedDRA term), and for the analysis of concomitant medications, all vaccinated subjects will be considered. Subjects who did not report the event or the concomitant medication will be considered as subjects without the event or the concomitant medication respectively.

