11.2.5. Safety

In case there will be more than 5% of subjects without documented dose for solicited symptoms (i.e., symptom screen not completed), sensitivity analysis will include only vaccinated subjects for doses with documented safety data (i.e., symptom screen completed).

For analysis of solicited, unsolicited adverse events (such as serious adverse events or adverse events by primary MedDRA term) and for the analysis of concomitant medications, all vaccinated subjects will be considered. Subjects who did not report the event or the concomitant medication will be considered as subjects without the event or the concomitant medication respectively.

The following rules will be used for the analysis of solicited symptoms:

- Subject who didn't document the presence or absence of a solicited symptom after one dose will be considered not having that symptom after that dose in the analysis done on "administered dose"
- Subjects who documented the absence of a solicited symptom after one dose will be considered not having that symptom after that dose.
- Subjects who documented the presence of a solicited symptom and fully or partially recorded daily measurement over the solicited period will be included in the summaries at that dose and classified according to their maximum observed daily recording over the solicited period.
- Subjects who documented the presence of a solicited symptom after one dose without having recorded any daily measurement will be considered as having that symptom after that dose (at the lowest intensity).
- Intensity of the following solicited AEs will be assessed as described in [Table 8](#) and [Table 9](#).

Table 8 Intensity scales to be used by the parent(s)/LAR(s) for solicited symptoms during the solicited follow-up period

Adverse Event	Intensity grade	Parameter
Fever*		Record temperature in °C/°F using any age-appropriate route.
Irritability/Fussiness	0	Behavior as usual
	1	Crying more than usual/no effect on normal activity
	2	Crying more than usual/interferes with normal activity
	3	Crying that cannot be comforted/prevents normal activity
Diarrhea\$		Record the number of looser than normal stools/day
Vomiting§		Record the number of vomiting episodes/day
Loss of appetite	0	Appetite as usual
	1	Eating less than usual/no effect on normal activity
	2	Eating less than usual/interferes with normal activity
	3	Not eating at all
Cough/runny nose	0	Normal
	1	Cough/runny nose which is easily tolerated

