Solicited general symptom	Primary analysis: all subjects with study vaccine administered Sensitivity analysis: all subjects with at least one solicited general symptom documented as either present or absent (i.e., symptom screen completed)	Primary analysis: all study visits with study vaccine administered Sensitivity analysis: all study visits with study vaccine administered and with at least one solicited general symptom documented as either present or absent (i.e., symptom screen completed)
Unsolicited symptom	All subjects with study vaccine administered	All study visits with study vaccine administered
Concomitant medication	All subjects with study vaccine administered	All study visits with study vaccine administered

For summaries by MedDRA primary preferred term combining solicited and unsolicited adverse events, solicited adverse events will be coded as per the following MedDRA codes

Solicited symptom	Lower level term code	Corresponding Lower level term decode
Fever	10016558	Fever
Irritability/Fussiness	10022998	Irritability
Diarrhoea	10012727	Diarrhoea
Vomiting	10047700	Vomiting
Loss of appetite	10003028	Appetite lost
Cough/runny nose	10011224	Cough

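### Undocumented solicited symptoms are scored as absent, and the documented-dose re-analysis depends on two 5% triggers, in different units, that can disagree on the same data

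*SAP*

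**What the plan says.** Scoring rule. Protocol 10.5 keeps all vaccinated subjects in the safety denominators and states: "Subjects who did not report the event or the concomitant medication will be considered as subjects without the event". SAP 6.4.2 and 11.2.6 repeat the rule. For solicited symptoms, SAP 11.2.5 says that a subject who did not document the "presence or absence of a solicited symptom after one dose will be considered not having that symptom after that dose" in the administered-dose analysis.

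Re-analysis. SAP 6.4.2 plans a sensitivity analysis on documented doses, to be run "in case more than 5% of the doses are not documented". SAP 11.2.5 gives a different condition: "In case there will be more than 5% of subjects without documented dose for solicited symptoms". Neither section says whether the 5% is taken within each arm or over both. The table in 11.2.5 gives the per-dose denominator of this analysis as "all study visits with study vaccine administered and with at least one solicited general symptom documented as either present or absent".

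Diary cards. Protocol 5.6.13 and Table 4 issue cards at the two HRV visits only (Visits 1 and 2), have them returned at the next visit, and require unreturned cards to be sought.

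Descriptive tables. SAP Template 17 lays out symptom-sheet return by dose and group on the Exposed Set. SAP 5.3 lists an HRV dose with an undocumented solicited symptom as an important deviation reported by group, and SAP 6.1.2 provides that summary for the PPS.

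**The concern.** Scoring an unreturned card as symptom-free biases the rate in a known direction. The planned analysis that would show the size of the bias may or may not be produced, depending on which SAP section is followed. If the two sections give different answers, someone has to choose between them at the final analysis, when the data are in hand.

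Solicited symptoms are a secondary endpoint, reported side by side for the new formulation and the licensed one. If card return differed between arms, the scoring rule would turn that difference into an apparent difference in tolerability. Site staff know the assignment (Protocol 5.3) and also chase and transcribe the cards, so unequal return is possible, although nothing in the documents shows that it is expected.

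**Working it through.** **Denominators.** Protocol 10.3 gives 832 evaluable subjects and 35% non-evaluable: 832 / (1 − 0.35) = 1280, and 416 / 0.65 = 640 per arm. The enrolment target is reproduced. Assuming that every infant receives both HRV doses, there are 2 × 1280 = 2560 diary-covered doses, or 1280 per arm.

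**Thresholds, taken as pooled.** Dose rule (6.4.2): 0.05 × 2560 = 128, so it fires from 129 undocumented doses. Subject rule (11.2.5): 0.05 × 1280 = 64, so it fires from 65 subjects. The subject rule can mean infants with *any* undocumented dose or infants with *no* documented dose.

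| Pattern | Undocumented doses | Dose rule | Subject rule, any missing | Subject rule, none documented |
|---|---|---|---|---|
| 65 infants miss one card | 65/2560 = 2.54% | no | 65/1280 = 5.08%, yes | 0%, no |
| 129 infants miss one card | 129/2560 = 5.04% | yes | 129/1280 = 10.08%, yes | 0%, no |
| 64 infants miss both | 128/2560 = 5.00% | no | 64/1280 = 5.00%, no | 5.00%, no |
| 65 infants miss both | 130/2560 = 5.08% | yes | 65/1280 = 5.08%, yes | 5.08%, yes |

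The first row sets the dose rule against the *any* reading. The second sets it against the *none* reading. Each reading therefore conflicts with Section 6.4.2 for some data.

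**Size of the bias.** If infants without a card have the same symptom rate as the others, then per dose: scored rate = true rate × documented share. The documents give no expected symptom rates, so 70%, 25% and 3% are assumptions that span common to rare symptoms.

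- 5% undocumented in both arms: 70% × 0.95 = 66.5%; 25% × 0.95 = 23.75%; 3% × 0.95 = 2.85%.
- All 128 permitted doses in one arm, 128/1280 = 10% of its doses, with equal true rates: 70% × 0.90 = 63.0% (artificial difference 7.0 points); 25% × 0.90 = 22.5% (2.5 points); 3% × 0.90 = 2.7% (0.3 points).
- A dose trigger applied within each arm would cap the artificial difference at 0.05 × 70% = 3.5 points.
- 0.5% undocumented: 70% × 0.995 = 69.65%, which is negligible.

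**Would the subject rule catch the 7-point case?** On the *none* reading, no: 128 doses can leave at most 64 infants without any card, 64/1280 = 5.00%, which is not above 5%. On the *any* reading it stays silent only if the same 64 infants missed both cards. If 128 infants each missed one, 128/1280 = 10% and it fires.

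**What a dose is.** SAP 11.2.2 numbers doses by vaccination visit, and Visit 3 is a vaccination visit without a card. Read literally, 1280 of 3 × 1280 = 3840 visits (one third) are undocumented by design and the dose trigger would always fire. The endpoint is defined after HRV doses, so this is unlikely to be the intent, but the trigger does not say so.

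**The case against.** The strongest reply is that the all-vaccinated rule is prespecified in the protocol, that the SAP already goes further by adding a sensitivity analysis, and that the mismatch in units is a drafting slip. Template 17 carries no 5% condition and would show return by dose and group. Undocumented symptoms are reported by group as deviations. Sites must chase unreturned cards, and the parents who complete them are blinded. The endpoint is summarised within group with exact intervals, without a between-group test or margin.

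Most of this stands, and it limits the point. A reader might infer that unbalanced missingness would go unseen. The documents do not support that, because the compliance layout would reveal it. A reader might also infer that 5% missingness always passes without a re-analysis, or that the two triggers always conflict. Neither holds: the outcome depends on the pattern of missing cards and on the reading of 11.2.5. Differential return is possible but not evidenced. In the other direction, the compliance of 99.3% to 100% printed in Template 17 is mock content that refers to several vaccine lots, so it does not show that return will be near complete here.

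Two things survive. The compliance and deviation tables describe missingness but do not give a corrected symptom rate. The deviation summary is on the PPS, whereas safety uses the Exposed Set. Infants who stop early, plausibly the ones who do not return cards, leave the PPS for an incomplete vaccination course or missing serology (SAP 5.2.2.1).

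**Conclusion.** The point holds as a low-severity improvement. The scoring rule lowers reported incidence whenever a symptom occurred and was not documented. The only planned re-estimation hangs on two rules that can give opposite answers. Under a pooled dose trigger, a relative understatement of 5% in both arms, or of 10% in one arm, can pass without that trigger firing. At an assumed 70% rate this is 3.5 points in each arm, or an artificial 7-point difference.

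These sizes rest on the assumed symptom rates, on full two-dose vaccination, and on equal symptom rates in infants with and without cards. If parents of well infants return fewer cards, the bias is smaller. For rare symptoms or near-complete return it is trivial.

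Two stronger conclusions might be drawn, and neither follows. The first is that the trial's main findings are at risk. Protocol 10.9 and SAP 7 make everything outside the co-primary objectives descriptive, so no co-primary conclusion is touched. The second is that the documented-dose analysis should replace the main one. That would depart from Protocol 10.5 and exchange one possible bias for another, since documented doses are themselves a selected set if return depends on symptoms.

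**What to change.** In SAP 6.4.2 and 11.2.5, delete both 5% conditions. State that solicited symptoms will also be analysed on documented doses, unconditionally and by arm, with HRV doses (Visits 1 and 2, where cards are issued) as the per-dose denominator. Keep the protocol's all-vaccinated analysis as the main table, so the protocol need not change.

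The cost is one extra set of descriptive tables, whose denominators the SAP already gives apart from the restriction to HRV doses. Two limits remain. The added analysis can be selective if return depends on symptoms, so it should be read beside the main table and the compliance table. Also, a dose counts as documented once a single symptom is recorded, so blanks for other symptoms on a partly completed card stay in the denominator and, under the general rule in SAP 11.2.6, count as absent.

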7. ANALYSIS INTERPRETATION

Except for analyses addressing criteria specified in the co-primary objectives referred as confirmatory analyses, all the analyses will be descriptive/exploratory in nature. The use of these descriptive/exploratory analyses should be limited to support the confirmatory analyses or to generate hypothesis.

7.1. Control on type I error

A 2.5% nominal type I error will be used for each co-primary evaluation. To control the type I error below 2.5%, a hierarchical procedure will be used for the multiple study objectives. That is, an objective will be reached if its associated criterion is met and the previous objectives were reached. The same order in which the study objectives are listed in Section 3.1 will be considered for hypothesis testing.

8. CONDUCT OF ANALYSES

8.1. Sequence of analyses

Safety data that is as clean as possible will be analyzed for IDMC review. Details of the review are described in an IDMC charter. The final analyses of all data will be conducted after conclusion of the ESFU contact and will include the final analyses of immunogenicity, reactogenicity and safety.

The following table provides the plan for analyses excluding analyses dedicated to IDMC

Description	Analysis ID	Disclosure Purpose (IN=internal, CTRS=public posting, SR=study report and public posting)	Dry run review needed (Y/N)	Study Headline Summary (SHS)requiring expedited communication to upper management (Yes/No)	Reference for TFL
Final	E1_01	SR	Yes	Yes	TFL TOC first version - All TFLs

8.2. Statistical considerations for interim analyses

Not applicable

9. CHANGES FROM PLANNED ANALYSES

The planned analysis of the percentage of doses and of subjects reporting at least one grade 3 causally related symptom (solicited or unsolicited) during the 8 day (Day 1-Day 8) solicited follow-up period post-vaccination will not be generated considering this analysis is of limited clinical relevance and is not part of the standard analyses planned in other PCV free Rota studies.

10. LIST OF FINAL REPORT TABLES, LISTINGS AND FIGURES

The TFL TOC provides the list of tables/listings and figures needed for the study report. It also identifies the tables eligible for each analyses and their role (synopsis, in-text, post-text, SHS, CTRS). Note that all TFL aimed to be included as post-text are noted as post-text even if these are tabulation of individual data such as listing of SAE. The post-text material contains all source material for the study report and accordingly a post-text table may be redundant with an in-text table.

The mock tables referred under column named 'layout' can be found in Annex 3:of this SAP.

The following group names will be used in the TFLs, to be in line with the T-domains:

Group order in tables	Group label in tables	Group definition for footnote
1	Liq	PCV-free-HRV liquid vaccine co-administered with Pediarix, Hiberix and Prevenar 13
2	Lyo	HRV Lyophilised vaccine co-administered with Pediarix, Hiberix and Prevenar 13

11. ANNEX 1 STANDARD DATA DERIVATION RULE AND STATISTICAL METHODS

11.1. Statistical Method References

The exact two-sided 95% CIs for a proportion within a group will be the Clopper-Pearson exact CI [Clopper CJ, Pearson ES. The use of confidence or fiducial limits illustrated in the case of binomial. *Biometrika*. 1934;26:404-413].

The standardised asymptotic two-sided 95% CI for the group difference in proportions is based on the method described in the following paper: Robert G. Newcombe, interval estimation for the difference between independent proportions: comparison of eleven methods, *Statist Med*. 1998; 17, 873-890]. The standardised asymptotic method used is the method six.

11.1.1. Pertussis vaccine response analysis

Usually immunological titres above t^* , a fixed cut-off, are used as surrogate of efficacy. Therefore, non-inferiority of a new vaccine is claimed when $P(t^*)$, the proportion of subjects with post-vaccination titres above t^* , is not decreased as compared to a control vaccine by more than Δ , a pre-specified non-inferiority margin.

For pertussis non-inferiority on seroresponse,

let $P_i(t^*)$ be the percentage of subjects with titer above t^* in group i, i=1 for Liquid and i=0 for lyo), the null hypothesis can be written as,

$$H_0: P_1(t^*) < 85\% = 95\% - \Delta$$

with t^* calibrated so that $P_0(t^*) = 95\%$

Would t^* be fixed, the p-value would be computed from a binomial distribution with probability=85%, N=number of subjects in group Liquid and n=the number subjects with titer above t^* .

As t^* is random, the expected p-value can be computed accounting for the distribution of t^* as $\int \Pr\{ \text{Bin}(n_1, \tau - \Delta) > n_1 P_I(t^*) \} f_0(t^*) dt^*$

with $f_0(t^*)$ denoting the distribution of t^* .

Based on the hypothesis testing principle that the type I error is the expected percentage of falsely rejecting H_0 when H_0 is true, the proposed test is to reject H_0 when the expected p-value is below the type I error.

The distribution of $f_0(t^*)$ will be estimated using a non-parametric bootstrapping (1000 repetitions) approach.

The operating characteristics of the method was assessed via simulations. The log-transformed antibody titre of a subject in study group i was obtained from a normally distributed random function with mean and variance (μ_i, σ^2_i) ($i=0$ for the control group).

To simulate data under the condition that $P_I(t^*) = \tau - \Delta_A$, the values of μ_0, σ_0, μ_I , and σ_I were constraint so that $\mu_0 + \sigma_0 Z_\tau = \mu_I + \sigma_I Z_{\tau - \Delta_A}$ with Z_τ denoting the Probit function.

Simulations were done under 2 conditions:

- The null hypothesis that $P_I(t^*) = \tau - \Delta$: This allowed estimating the true type I error rate of tests supposed to control the type I error below 2.5%. This was estimated by the proportion of simulations for which the p-value rejected $H_0: P_I(t^*) < \tau - \Delta$ at significance level 2.5%
- The alternative hypothesis that $P_I(t^*) = \tau - \Delta_A$: This allowed estimating the power of the tests. This was estimated by the proportion of simulations for which the p-value rejected $H_0: P_I(t^*) < \tau - \Delta$ at significance level 2.5%

The simulation also included power and type I estimation when using Miettinen non-inferiority p-value with 10% margin. The simulation indicated that the proposed stat method controlled well the type I error.

Table 6 Power for a non-inferiority margin $\Delta = 10\%$, $P_0(t^*) = 95\%$ and a 2.5% significance level

μ_0	$\sigma_0 = \sigma_1$	n_0	μ_1	n_1	$P_1(t^*)$	P_{vals}	P_{val_n}
Impact of n_0							
0	1	100	0	300	95%	94.2%	77.9%
0	1	150	0	300	95%	96.3%	89.7%
0	1	300	0	300	95%	99.4%	98.1%
Impact of σ_0							
0	1	300	0	300	95%	99.4%	98.1%
0	10	300	0	300	95%	99.5%	98.6%
0	100	300	0	300	95%	99.4%	98.5%
Impact of true difference							
0	1	300	-.2	300	92.575%	90.9%	75.8%
0	1	300	-.3	300	91.066%	71.5%	45.1%
0	1	300	-.4	300	89.341%	47.8%	21.7%
Impact of n_1							
0	1	300	-.3	250	91.066%	68.8%	45.2%
0	1	300	-.3	200	91.066%	61.5%	40.8%
0	1	300	-.3	150	91.066%	53.4%	33.2%

 P_{vals} = Power for the traditional method (Miettinen, 1985). The method assumes that t^* is fixed P_{val_n} = Power for the proposed method**Table 7 Type I error for a non-inferiority margin $\Delta = 10\%$, $P_0(t_0) = 95\%$ and a 2.5% significance level**

μ_0	σ_0	n_0	μ_1	σ_1	n_1	$P_1(t^*)$	P_{vals}	P_{val_n}
0	1	300	-0.6084	1	300	85%	7.9%	0.8%
0	1	300	0	1.5870	300	85%	3.2%	0.9%
0	1	300	-0.2	1.3941	300	85%	3.1%	0.9%

 P_{vals} = type I error for the traditional (method Miettinen, 1985). The method assumes that t^* is fixed. P_{val_n} = type I error for the new method

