Seroresponse to PRN\$	10.0%	0.409	416	416	0.1%
Global Power > 90.0%					

N = Number of evaluable subjects per group, Anti-D = anti-diphtheria antibody, Anti-T = anti-tetanus antibody, Anti-IPV1 = anti-poliovirus type 1, Anti-IPV2 = anti-poliovirus type 2, Anti-IPV3 = anti-poliovirus type 3, Anti-PT = anti-pertussis toxoid antibody, Anti-FHA = anti-filamentous hemagglutinin, Anti-PRN = anti-pertactin antibody, Anti-PRP = antibodies against polyribosyl-ribitol-phosphate; Anti-HBs = antibodies against hepatitis B.

For Anti-PRP, anti-D, anti-T, anti-IPV1, anti-IPV2 and anti-IPV3 antibodies, the reference used for power calculation is rate. For the rest of the antibodies, the standard deviation values were considered.

*For rates ~100%, a conservative reference of 99.5% is taken.

\$Power results were based on the simulation assuming the distribution of immune response from *HRV Liq group* and *HRV Lyo group* are the same, and equal sero-response rate between groups under the alternative (seroresponse for

anti-PT, anti-FHA and anti-PRN in *HRV liq* group were defined as the percentage of subjects showing an antibody concentration above a threshold that led to 95% seroresponse in the *HRV lyo*), 1-sided, alpha=0.025.

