- The lower limit of the two-sided standardized asymptotic 95% CI on the difference between groups (HRV Liq group minus HRV Lyo group) in the percentages of subjects with concentration of antibodies against anti-PRP $\geq 1.0 \mu\text{g/mL}$ is $\geq 10\%$ (clinical limit for non-inferiority).

- To rule out a 10% decrease in seroresponse to PT, FHA and PRN antigen when *Pediarix* is co-administered with PCV-free-liquid HRV vaccine compared to when *Pediarix* is co-administered with the currently licensed lyophilized HRV vaccine.
 - seroresponse is defined as the percentage of subjects showing an antibody concentration above a threshold that leads to 95% seroresponse in the control group (lyophilized HRV vaccine),
 - p-value on the difference in seroresponse between groups is $<2.5\%$ for each PT, FHA and PRN antigen (p-value is computed by integrating on the p-value for the null hypothesis that the seroresponse rate in the liquid group is $<85\%$ and the a-posteriori probability of the threshold in the lyophilized group).

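### The printed formula for the pertussis seroresponse p-value leaves out the observed count, so the p-value is too small by one averaged binomial term; this is a minor correction, not a shown loss of type I error control

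*SAP*

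**What the plan says.** SAP 3.1 sets the second co-primary objective: "To rule out a 10% decrease in seroresponse to PT, FHA and PRN antigen". Response means an "antibody concentration above a threshold that leads to 95% seroresponse in the control group (lyophilized HRV vaccine"), and p must be below 2.5% for each of the three antigens. SAP 7.1 adds: "A 2.5% nominal type I error will be used for each co-primary evaluation". The notes to Protocol Table 18 give the test as "1-sided, alpha=0.025".

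The working definition of the p-value is in SAP 11.1.1. For a fixed threshold, "the p-value would be computed from a binomial distribution with probability=85"%. Since t* is random, "the expected p-value can be computed accounting for the distribution of" t*: the SAP averages Pr{Bin(n1, tau - Delta) > n1 P1(t*)} over that distribution, which "will be estimated using a non-parametric bootstrapping (1000 repetitions) approach". It rejects when this average is below the type I error. It concludes: "The simulation indicated that the proposed stat method controlled well the type I error". The support is SAP Table 7, which gives 0.8%, 0.9% and 0.9% at 300 per arm.

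Sections 6.3.1.2 and 6.3.1.3 describe the test in words and do not say whether the tail includes the observed count. No section states which sample quantile defines t* in each bootstrap sample. There is no type I simulation at 416 per arm.

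**The concern.** A p-value for a null of at most 85% is the probability of the observed count or a larger one. With '>' the observed count is left out. In the extreme case, if every Liq infant exceeded t*, the formula would return exactly zero.

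A p-value just under 2.5% by the printed formula can be above 2.5% by the correct one. The result decides a co-primary objective that needs three such p-values. A programmer who follows Annex 1 literally would code the smaller value. Whether the resulting test still holds its 2.5% level then depends on how conservative the averaging over t* is, and on a quantile convention that the SAP leaves open.

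**Working it through.** **Inputs.** 416 evaluable subjects per arm (Protocol 10.3). Null rate 95% - 10% = 85%. One-sided alpha 0.025. Normal log titres, as in the SAP's own simulations. The SD ratio is Liq over Lyo.

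**1. The missing term, with t* held fixed.** Take 368 responders of 416.
- Printed: Pr(Bin(416, 0.85) > 368) = Pr(at least 369) = 1.77%.
- Correct: Pr(at least 368) = 2.52%.
- Difference: 2.52 - 1.77 = 0.75 points, which is Pr(exactly 368).

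So at this count the printed value passes and the correct one does not. In the planned test this term is averaged over the draws of t*.

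**2. The SAP's own Table 7 (300 per arm, true rate 85%).** The simulated size depends on tail and quantile. Since 0.05 x 300 = 15, both the 15th and the 16th ordered value are usual choices.

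| Rule | Size over the three scenarios |
|---|---|
| SAP Table 7 | 0.8 / 0.9 / 0.9% |
| '>=', 16th value | 0.79 / 0.95 / 0.89% |
| '>', 16th value | 1.15 to 1.37% |
| '>', 15th value | 1.7 to 2.2% |

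Table 7 is closer to '>='. An exact match cannot be claimed, because the SAP gives neither its number of simulated trials nor its quantile rule. Table 6 does not separate the two tails. For mean shifts 0, -0.2, -0.3 and -0.4 it reports 98.1, 75.8, 45.1 and 21.7%. The strict tail with the 16th value gives 98.4, 74.6, 47.2 and 21.8%. The inclusive tail with an averaged quantile gives 98.4, 75.6, 48.0 and 21.9%.

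**3. Size at the planned 416 per arm.** Exact bootstrap weights for t*, true rate 85%, SD ratios 1, 1.394, 1.587 and 2, 40,000 trials per setting:

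| t* in each bootstrap sample | '>' as printed | '>=' |
|---|---|---|
| 20th value | 2.7 to 2.9% | 2.1 to 2.2% |
| 21st value | 1.8 to 2.1% | 1.4 to 1.55% |
| 22nd value | 1.2 to 1.6% | 0.9 to 1.1% |

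Repeats with 30,000 trials moved these limits by about 0.1 point at most, giving up to 3.0% for '>' with the 20th value and up to 2.2% with the 21st.

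**4. Which value is t*?** 0.05 x 416 = 20.8. The 20th value leaves 396/416 = 95.19% above it, and the 21st leaves 395/416 = 94.95%. Common sample-quantile definitions return positions from 20.8 to 22, and none of the 13 checked returns 20. Interpolating at 20.8 gave about 2.1 to 2.3% with '>' (3,000 trials, so less precise).

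**5. Unequal SDs.** With '>' and the other quantile rules, size reaches 2.3 to 2.5% at an SD ratio of 3 and 2.6 to 2.9% at 5 or more. The widest ratios across reference groups in Protocol Table 17 are PT 0.297/0.257 = 1.16, FHA 0.293/0.255 = 1.15 and PRN 0.409/0.397 = 1.03.

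**6. Power at 416 per arm.** Under equality, '>' to '>=' moves power from 99.96 to 99.92% (20th value) or 99.89 to 99.87% (21st). A separate run gave 99.85 to about 99.81%. Protocol Table 18's type II error of 0.1% is compatible with either tail. At a true Liq rate of 91.07% (shift -0.3), power falls from 74.7 to 71.5% (20th), 68.8 to 65.2% (21st) or 62.5 to 58.7% (22nd).

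**The case against.** A reader might infer from the strict tail that the test breaks its 2.5% level at the planned sample size. The strongest reply is that the documents do not support this. The SAP treats t* as random and averages the p-value over it, and that averaging more than absorbs the missing term under ordinary quantile definitions. Figures above 2.5% from a fixed threshold (2.52% at 416, and up to about 3.5% for other Liq sizes between 380 and 479) do not describe the planned test. The large SD ratios that would also pass 2.5% are far from the reference SDs, and the notes to Protocol Table 18 assume the same distribution in both arms. The 20th value leaves slightly more than 95% above it, whereas the 21st is nearer to the 95% calibration in SAP 11.1.1. All of this stands.

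It can also be said that '>' is only notation. Table 7 fits '>=' better, and a '≥' lost in conversion to text cannot be excluded. That is possible but not shown. If it is so, the printed instruction differs from what was simulated and still needs correcting. The 20th value also remains open: an author who reads the definition as at least 95% strictly above t* would choose it.

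**Conclusion.** The p-value definition in SAP 11.1.1 is wrong as printed, by one averaged binomial term: up to about 0.75 points near the boundary at 416 per arm. This is a minor correction. With '>' the size is about 1.2 to 2.2% under common quantile definitions for SD ratios 1 to 2, and about 2.7 to 3.0% only if t* is the 20th ordered Lyo value. With '>=' it was below 2.5% for the 20th, 21st and 22nd values, so control no longer depends on which of these is programmed.

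Two stronger readings should not be taken from this. Loss of type I error control has not been demonstrated. Nor does Table 6 show which tail the sponsor simulated; only Table 7 leans towards '>=', and not conclusively. The simulated figures assume normal log titres and 416 evaluable infants in each arm.

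**What to change.** In SAP 11.1.1, replace the integrand by Pr{Bin(n1, 85%) >= n1 P1(t*)}. State which sample quantile defines t* in each bootstrap sample, including what is done when 5% of the arm size is not an integer. Re-run the type I simulation at 416 per arm with the code that will be used, and report the tail, the quantile rule and the number of simulated trials beside Table 7.

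The cost is one character in the SAP and program, one sentence on the quantile, and a short re-run of an existing simulation. Power falls by about 0.05 points under equality, the alternative used for the sample size, and by roughly 3 to 4 points if the true Liq rate is near 91%. The change should be made before the data are analysed.
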